2.0 TRIAL DESIGN

2.1 Trial Design

This is a phase II single arm efficacy/safety trial that will evaluate the effectiveness of combining intensive locoregional intraperitoneal (IP) chemoimmunotherapy of cisplatin with IP rintatolimod (TLR-3 agonist) and IV infusion of the checkpoint inhibitor pembrolizumab (IVP) for patients with recurrent platinum-sensitive ovarian cancer (OC).

Patient cohort

This trial will enroll up to 45 patients; eligibility criteria include patients at first or second recurrence previously diagnosed with platinum-sensitive ovarian/fallopian tube carcinoma or primary peritoneal carcinomatosis. Platinum-sensitive OC is defined as patients with a treatment-free interval greater than 6 months. Patients must have at least one peritoneal lesion, measurable by CT/MRI scan. Patients will be allowed if RECIST 1.1 criteria is met for measurable retroperitoneal lesions if there also is the presence of peritoneal lesions during laparoscopy. The lesion should be large enough for biopsy and resection, ideally to yield greater than 2 grams of tumor for immunoassays. If biopsy is insufficient or not feasible during laparoscopy, patients may be allowed to proceed at the discretion of the PI if there are otherwise measurable lesions. All epithelial invasive histologies are included in this phase II design.

Patients will receive a total of six treatment cycles, at 3-week intervals (Schema 1, Section 2.2). We will use an IP neoadjuvant approach, followed by interval cytoreduction (usually laparoscopically) of residual tumor. The decision to perform interval cytoreductive surgery is at

the discretion of the treating physician. Cytoreduction will occur approximately 4 weeks after the fourth treatment cycle. Post-surgery we will consolidate with 2 additional courses of same chemo-immunotherapy regimen. Catheter will be removed 12 weeks after the last treatment. All surgical procedures, if done laparoscopically, are outpatient and will yield up to three serial biopsies of the tumor sites: 1) at catheter placement; 2) at interval cytoreduction which consists of removal of any visible tumor sites and the site biopsied initially whether tumor is present or not; 3) at catheter removal, when site of first tumor biopsy will be re-biopsied for pathologic response.

[figure not shown]
5

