3.0 OBJECTIVE(S) & HYPOTHESIS(ES)

3.1 Primary Objective(s) & Hypothesis(es)

(1) **Objective:**

This phase II trial will consist of up to 45 evaluable patients to specifically define the clinical efficacy and impact on immunologic efficacy endpoints of IP cisplatin/rintatolimod and IV pembrolizumab. Primary clinical efficacy endpoint will be objective response rate by RECIST

6

1.1 criteria at 13 weeks (CT imaging at 7 weeks and 13 weeks) as compared to historical controls. The trial schema encapsulates a trial design similar to our recent phase I SPORE trial (UPCI 11-128/NCT02615574, [name] - Clinical PI; [name]- Translational PI) in which intraperitoneal cisplatin and rintatolimod was well tolerated and induced favorable immune response on interim analysis.

The strategy of combining pembrolizumab with IP cisplatin/rintatolimod is to induce cell death and cell damage of the peritoneal tumor implants with chemotherapy followed by locoregional and systemic modulation of innate and adaptive immune effectors to further promote immune clearance of remaining tumor.

Objective/Pathologic Response

Imaging will be performed at baseline, two weeks after cycle 2 and cycle 4 for objective responses by RECIST 1.1 criteria. Imaging will again be performed 4-6 weeks after completion adjuvant chemotherapy for baseline post treatment. Between 2 months after successful completion of the trial, the IP port will be removed laparoscopically. During the IP port removal, a second-look treatment effect evaluation and biopsy for pathologic response will be performed.

Disease Progression

Progression during trial will be assessed by iRECIST. If there is confirmed progression prior to interval surgery, patients will not undergo interval surgery, just IP port removal and biopsy after confirmed progression by iRECIST. Patients will be followed for 3 years or until recurrence after completing treatment to determine time to progression (TTP), ratio of progression-free interval (PFI) as compared to their initial PFI, and survival will be a secondary efficacy endpoint. Follow-up data will be used to estimate progression-free and overall survival at 3 years.

Biological Endpoints

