The primary endpoint is the objective response rate (rate of CR+PR by RECIST 1.1) at 13 weeks. Based on Ten Tije and Wils et al, the intent-to-treat objective response rate for IP cisplatin alone in platinum-sensitive recurrent ovarian cancer was approximately 45% 51 . An increase from 45% to 65% among response-evaluable patients would be of sufficient interest to warrant further study of the addition of rintatolimod and pembrolizumab in the presence of an acceptable safety profile. An optimal Simon two stage design with $\alpha = \beta = .10$ has been selected that will require 20 patients in the first stage and 25 in the second. In the first stage, 12 patients must have a response (PR or CR) in order to continue to the second stage. If the trial continues to the second stage and accrues 25 more patients and there are 25 or more patients with an objective response among the total of 45 treated, the study will be considered successful at demonstrating increase efficacy compared to cisplatin alone. The probability of early termination if the response rate is 45% is .59.

Continuous Monitoring of RLTs during the Study

Subject safety will be monitored continuously using Bayesian methods. If the posterior probability is .80 or greater that 30% or more of treated subjects experience a treatment related RLT as defined above, the RLT rate would be unacceptable and the study will be suspended pending review by the DSMC. This posterior probability will be calculated from the study's accumulating data and a weakly informative prior distribution. If π denotes a random variable representing the proportion of subjects who will experience a treatment related RLT, we assume π has a beta distribution with parameters a = 1.2 and b = 2.8 which assumes a mean of 30%. The table below describes the number of RLTs per number of treated patients that would trigger suspension. The table also shows the posterior probability that the RLT rate exceeds 33% and the binomial probability associated with the decision for an assumed 33% RLT rate.

Table 8: Number of RLTs per Number of Patients Treated Needed to Trigger Suspension

Subjects	Treatment-Related RLTs	$PP(\pi > 30\%)*$	$Pr(X \ge r p = .30)$
6	4	.903	.070
9	5	.904	.099
12	6	.890	.118
15	7	.880	.131
17	8	.903	.105
20	9	.896	.113
23	10	.891	.197
26	11	.886	.125
29	12	.883	.129
32	13	.880	.133

35	14	.877	.135
38	15	.876	.137
41	16	.874	.138
44	17	.873	.139

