8.2 Statistical Analysis Plan

Proposed Data Analysis Primary Objectives

Objective response rate and progression-free based on RECIST 1.1 criteria (RC) will be estimated with 90% confidence intervals. The objective response rate (ORR) will be estimated by the proportion of subjects with the best response of complete response (CR), or partial response (PR) by RC, with corresponding exact 90% confidence limits being reported.

Proposed Data Analysis Secondary Analysis

The progression-free survival (PFS) will be measured from the initial date of the study treatment to the date of documented tumor progression using RC, or the date of death in the absence of tumor progression. PFS will be estimated by the Kaplan-Meier method with Greenwood 90% confidence intervals

Within-patient changes in CD8+ cells will be measured in tumor tissue and in peritoneal fluid at weeks 1,8, and 12. Mixed linear models will be used to estimate changes from baseline.

An assessment of the association among immune parameters, and ORR will be conducted. Endpoints for analysis include (CTL, NK- and Th1 cells) in the peritoneal fluid and resected residual tumor mass The panel of immune parameters will be tested for association with objective response with the Jonckheere-Terpstra test for trend by ordering response 1-4 for PD, SD, PR and CR, respectively. Significant association will be adjusted for initial tumor grade, and the interval between initial diagnosis of OC and protocol accrual. To guard against false positive results, the estimated false discovery rate will be calculated by the method of Benjamini and Hochberg (J. R. Statist. Soc. B Vol 57, No 1, 289-300, 1995).

HCC 18-087 Version Dated 5-20-2021

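### The 65% target is set on an undefined evaluable set while the null and success rule use treated patients, so the 90% power holds only for 65% of treated; separately, the printed 12/20 first-stage gate contradicts the stated design

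*Combined protocol and SAP*

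**What the plan says.** Section 8.1 (Efficacy Study Design and Endpoints) gives the historical benchmark on an intent-to-treat basis: "the intent-to-treat objective response rate for IP cisplatin alone in platinum-sensitive recurrent ovarian cancer was approximately 45"%. The next sentence sets the improvement of interest on a different basis: "An increase from 45% to 65% among response-evaluable patients would be of sufficient interest to warrant further study". An optimal Simon two-stage design with α = β = .10, 20 patients and then 25, follows from these two rates.

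The decision rules are:
- Stage 1: "In the first stage, 12 patients must have a response (PR or CR) in order to continue to the second stage".
- Final: success if "there are 25 or more patients with an objective response among the total of 45 treated".
- Stated property: "The probability of early termination if the response rate is 45% is .59".

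Elsewhere the 45 patients carry other labels. Section 3.1 says "This phase II trial will consist of up to 45 evaluable patients", and Section 2.1 says "This trial will enroll up to 45 patients". For the reported estimate, Section 8.2 says "The objective response rate (ORR) will be estimated by the proportion of subjects with the best response of complete response (CR") or partial response, with exact 90% limits. It names no analysis set beyond subjects. Response-evaluable is not defined anywhere, and no allowance is made for non-evaluable patients.

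**The concern.** This is a single-arm trial whose only comparison is with a historical rate, so the null, the target, the boundaries and the reported response rate need one denominator. If some treated patients cannot be assessed, 65% of the evaluable patients is less than 65% of the treated patients. The rule counts responders among those treated, so the design would then be less sensitive than stated to the very improvement the plan calls worthwhile. The response rate in Section 8.2 could also be reported on more than one denominator.

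A second problem sits in the same paragraph. The printed first-stage gate does not produce the stated early-termination probability. This gate decides whether the trial continues, and every power figure depends on it.

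**Working it through.** **Inputs (Section 8.1).** p0 = .45, p1 = .65, n1 = 20, n2 = 25, success at 25 or more of 45, printed gate 12/20, stated early termination .59 at 45%, α = β = .10. The non-evaluable share d is not in the documents; every value of d below is an assumption.

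**Formulas.** With gate g and response probability p per treated patient:
- P(stop early) = P(Bin(20, p) ≤ g − 1)
- P(success) = Σ over x from g to 20 of P(Bin(20, p) = x) × P(Bin(25, p) ≥ 25 − x)

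**Step 1: reproduce the plan's own figures.**

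| Gate | Early termination at .45 | Type I error at .45 | Power at .65 |
|---|---|---|---|
| Stated | .59 | .10 at most | .90 at least |
| 10 or more of 20 | .5914 | .0903 | .9001 |
| 12 or more of 20 (printed) | .8692 | .0533 | .7459 |

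An exhaustive search for the optimal Simon design (total size up to 52) returns n1 = 20, continue at 10 or more, N = 45, success at 25 or more. The stated design therefore has a gate of 10. With the printed 12, power falls short by .90 − .746 = .154 even if every patient is evaluable.

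**Step 2: which population the 90% belongs to.** The rule counts responders among 45 treated, so p is a rate per treated patient. The .9001 is power for 65% of treated patients, and the margin over .90 is .0001.

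**Step 3: read 65% as a rate among evaluable patients (gate 10).** Non-evaluable patients stay among the 45 and cannot be responders.

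Exactly one such patient:
- in stage 2 (20 + 24 evaluable): power .8775
- in stage 1 (19 + 25 evaluable): power .8539

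As an assumed share, p = .65 × (1 − d):

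| d | p | Power |
|---|---|---|
| 0 | .6500 | .9001 |
| 1/45 | .6356 | .8629 |
| 5% | .6175 | .8044 |
| 10% | .5850 | .6675 |

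The loss from a single patient comes from the two-stage rule. The final boundary alone, without a first-stage gate, has power .929 with 45 evaluable patients and .901 with 44.

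**Step 4: type I error.** The null is already intent-to-treat and the count is among treated patients, so p = .45 applies directly. Type I error is .0903 with gate 10, or .0533 with the printed gate.

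**The case against.** - **The decision rule already deals with missing assessments.** A treated patient with no documented response stays in the 45 and adds nothing to the 25. This is right. It leaves open only which population the 65% and the 90% power describe, and which denominator Section 8.2 uses.
- **Non-evaluable patients may be rare.** Section 5.1.1 requires measurable disease, and Section 7.1.2.6.1 has the site confirm it on screening images. Scans are due at weeks 7 and 13 by calendar date, and Section 7.1.2.6.2 asks for imaging at discontinuation. This stands, and the 10% row has no support in the documents. Zero cannot be assumed either: Section 5.6 lists loss to follow-up among the reasons for discontinuation.
- **The target sentence can be read as putting both rates on the evaluable set.** Grammatically it can. It would then conflict with the preceding sentence and with the treated-patient success rule, so the wording still needs correction.
- **The power losses in Step 3 use a gate that the plan does not print.** True. Gate 10 is inferred from .59 and from the design search. With the printed gate, power is below .90 before evaluability enters.

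Three stronger readings are tempting and are not supported:
- *Denominator mixing alone puts power below 90%.* This needs both the evaluable reading of 65% and at least one non-evaluable patient.
- *The false-positive rate is inflated because non-evaluable patients would be replaced until 45 are evaluable.* No section provides for replacement. Whether 45% is also the evaluable rate in the historical series depends on a source not reproduced here.
- *Excluding a few patients could lift the lower confidence limit above 45% and so produce success.* Success is a count of responders. The 90% interval is not the decision criterion, and no section provides for exclusions.

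**Conclusion.** The concern holds in a limited form. The plan uses an intent-to-treat null, an evaluable target and a treated-patient count without defining the evaluable set. Type I error is not affected. The 90% power is correct for 65% of treated patients at the inferred gate of 10/20. It drops below .90 if 65% refers to evaluable patients and even one treated patient is non-evaluable: to .8775 or .8539 with one, and to .804 at an assumed 5%. These losses assume that non-evaluable patients remain among the 45. How large the loss would be is unknown, because the documents give no share.

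The conflict over the first-stage gate is the larger and certain defect. As printed, a regimen with a true 65% response rate succeeds with probability .746, and one at 45% is stopped early with probability .869, against the stated .90 and .59. Both matters should be fixed; the gate comes first, because the other power figures depend on it.

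**What to change.** 1. Reconcile the first-stage gate in Section 8.1 with the stated .59 and α = β = .10. A gate of 10 or more of 20 reproduces those figures. If 12 is intended, restate early termination, type I error and power as .869, .053 and .746.
2. Name all patients who start study treatment as the single primary set for the null, the target, both boundaries and the response rate with its exact 90% interval in Section 8.2. Count a patient with no post-baseline response assessment as a non-responder.
3. Delete the response-evaluable qualifier in Section 8.1 and the word evaluable in Section 3.1. If the sponsor prefers an evaluable target, keep it and restate the lower power with the assumed share.
4. Define the evaluable set, and report its response rate only as a sensitivity analysis with its denominator.

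The cost is wording in Sections 3.1, 8.1 and 8.2, with no new data. The scientific price is small. The target becomes slightly more demanding: with one patient in 45 non-evaluable, 65% of treated equals .65 / (44/45) = 66.5% of evaluable. The reported response rate may also be slightly lower. Keeping the evaluable target avoids this but means accepting the lower power.

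### The stage 1 rule of 12 responders in 20 does not belong to the Simon design the SAP states: it stops 87% of null trials, not 59%, and cuts power from 90% to 75%

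*Combined protocol and SAP*

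**What the plan says.** The efficacy design is given in one paragraph of Section 8.1 (Efficacy Study Design and Endpoints). The hypotheses come from this sentence: "An increase from 45% to 65% among response-evaluable patients would be of sufficient interest to warrant further study". The design is called an optimal Simon two-stage design with alpha and beta both equal to .10, and it "will require 20 patients in the first stage and 25 in the second". The interim rule reads: "In the first stage, 12 patients must have a response (PR or CR) in order to continue to the second stage". The final rule declares success if "there are 25 or more patients with an objective response among the total of 45 treated". The paragraph closes with one operating characteristic: "The probability of early termination if the response rate is 45% is .59". No other section gives a stage 1 threshold.

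**The concern.** With 20 patients and a 45% response rate, the expected number of responders is 9. A rule that continues only at 12 or more should therefore stop far more than 59% of null trials. The written interim bar (12/20 = 60%) is also higher than the final success bar (25/45 = 55.6%), which is odd for a rule meant to stop for futility.

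This is the binding go/no-go rule for the primary endpoint. With 10 or 11 responders the text says stop, while the stated error rates belong to a design that continues. Whoever had to settle that after seeing the count would be choosing the rule with the data in view.

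**Working it through.** **Inputs, all from Section 8.1.** Null rate p0 = .45; target rate p1 = .65; alpha = beta = .10; n1 = 20; n2 = 25; N = 45; success at 25 or more of 45; stated early termination .59 at 45%; written rule, continue at 12 or more of 20.

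**Formulas (exact binomial).** Let g be the smallest number of stage 1 responders that lets the trial continue.

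- Early termination: PET(p) = P(X1 ≤ g − 1), with X1 ~ Bin(20, p).
- Probability of declaring success: S(p) = Σ over x from g to 20 of P(X1 = x) · P(X2 ≥ 25 − x), with X2 ~ Bin(25, p). S(.45) is the type I error and S(.65) is the power.
- Expected sample size under the null: 20 + 25 · (1 − PET(.45)).

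**Step 1: reproduce the plan's figure.** P(X1 ≤ 9 | 20, .45) = .591, which is the stated .59. The written rule stops at 11 or fewer: P(X1 ≤ 11 | 20, .45) = .869.

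**Step 2: operating characteristics by go threshold** (success at 25 or more of 45):

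| Continue at | PET at 45% | Type I error | PET at 65% | Power |
|---|---|---|---|---|
| ≥ 9 | .414 | .098 | .020 | .921 |
| ≥ 10 | .591 | .090 | .053 | .900 |
| ≥ 11 | .751 | .075 | .122 | .847 |
| ≥ 12 (as written) | .869 | .053 | .238 | .746 |
| ≥ 13 | .942 | .031 | .399 | .594 |

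Only a threshold of 10 gives .59. Reading the text as more than 12 makes the gap wider.

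**Step 3: search for the optimal design.** An exhaustive search over total sizes from 25 to 65, for p0 = .45, p1 = .65, type I error at most .10 and power at least .90, was ranked on expected null sample size. The minimum is: stop at 9 or fewer of 20, reject at 24 or fewer of 45. Its expected null size is 20 + 25 · (1 − .5914) = 30.2, its type I error .0903 and its power .9001. This matches the SAP on stage sizes, final cut-off, alpha, beta and PET. The interim threshold is the only mismatch.

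**Step 4: where the power goes.** The two rules disagree only at 10 or 11 responders. At a true 65%:

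- P(X1 = 10) = .0686. Success then needs 15 or more of 25, which has probability .771.
- P(X1 = 11) = .1158. Success then needs 14 or more of 25, which has probability .875.
- Lost power = .0686 × .771 + .1158 × .875 = .154, which is .900 − .746.

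A 65% regimen lands on 10 or 11 with probability .0686 + .1158 = .184. At 45% the corresponding probability is .869 − .591 = .278.

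**The case against.** Four points can be made for the plan as written.

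First, the written rule is conservative. It lowers the type I error from .090 to .053, so a success declared under it would be sound. That is correct, and it limits the harm to lost power and wrongful stopping.

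Second, the sponsor may have wanted a stricter interim bar. The documents do not exclude this. But in that case the optimal-Simon label, the beta of .10 and the early-termination probability of .59 are all wrong, so the paragraph still cannot stand.

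Third, the correction has consequences. Against the written rule, a threshold of 10 raises expected enrolment under the null from 20 + 25 × (1 − .869) = 23.3 to 30.2, about 7 patients, within the same maximum. The summary also estimates enrolment in 2018-2019, while this version is dated May 2021, and the documents do not say whether stage 1 has been read. Both points bear on how the correction is made, not on whether it is needed.

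Fourth, the section refers both to response-evaluable and to treated patients, so the denominator is not fully settled. The stated .59 is for the same 20 stage 1 patients, so this does not explain the mismatch.

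**Conclusion.** The concern holds. Section 8.1 contradicts itself on the interim rule for the primary endpoint. As written, early termination at 45% is .869 rather than .59, and power at 65% is .746 rather than .90, so the type II error is about .25 instead of .10. The chance of dropping a truly 65% regimen at the interim is .238 rather than .053, more than four times as high. Type I error is not inflated.

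The figures assume independent patients with a common response rate, exactly 20 and 45 patients counted, and both rules followed as binding. A slip in the threshold is much the likeliest explanation, because all the other stated features agree on 10, but intent is inferred. This must be fixed, because the error sits in a rule that can end the trial.

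**What to change.** In Section 8.1, replace the stage 1 sentence with a rule that the trial continues if 10 or more of the first 20 patients respond and stops if 9 or fewer do. The remaining figures in the paragraph can then stay, and the attained values (type I error .090, power .900) can be added.

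If 12 is intended, keep it, remove the optimal-Simon label and the stated beta, and report early termination .87 at 45% and .24 at 65%, type I error .053 and power .75.

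In either case, the amendment should state whether the stage 1 count was known when it was written and, if stage 1 has been read, which threshold was applied. The choice should rest on the stated design, not on the observed count.

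The cost is a short amendment. The maximum stays at 45; with a threshold of 10, expected null enrolment is 30.2 instead of 23.3.

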7.0 TRIAL PROCEDURES

7.1 **Trial Procedures**

The Trial Flow Chart - Section 6.0 summarizes the trial procedures to be performed at each visit. Individual trial procedures are described in detail below. It may be necessary to perform these procedures at unscheduled time points if deemed clinically necessary by the investigator.

Given lack of information regarding safety and tolerability of this combination regimen, the first 3 patients should be staggered (second patient should not be able to begin treatment until 3 weeks after the first patient has begun the treatment, i.e. completed cycle 1, similarly third patient should not begin treatment until second patient has completed cycle 1). Moreover, patients should be observed for 3 weeks for DLTs

Furthermore, additional evaluations/testing may be deemed necessary by the Sponsor and/or Merck for reasons related to participant safety. In some cases, such evaluation/testing may be potentially sensitive in nature (e.g., HIV, Hepatitis C, etc.), and thus local regulations may require that additional informed consent be obtained from the participant. In these cases, such evaluations/testing will be performed in accordance with those regulations.

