8.0 STATISTICAL ANALYSIS PLAN

8.1 Statistical Analysis Plan Summary

Objectives

This trial will evaluate the anti-tumor efficacy of pembrolizumab in conjunction with IP cisplatin/rintatolimod. In addition to immunologic efficacy, a second objective is further monitoring of patient safety and adverse events. Provision is made to suspend the trial if unexpected and serious toxicities occur or if dose limiting toxicities (DLTs) from the list below in excess of 30% are observed:

- a) Any death not clearly due to the underlying disease or extraneous causes
- b) Any AE leading to a dose delay of greater than 14 days in initiation of cycle 2 will be considered a DLT
- c) A DLT is specifically defined as any of the following toxicities that occur related to any of the study interventions (cisplatin, rintatolimod, pembrolizumab) or the combination (as assessed by the Investigator) that occurs during the first cycle of treatment:
 - 1. Grade 3 renal toxicity
 - 2. Grade 2 or greater bronchospasm
 - 3. Grade 2 or greater allergic reaction or generalized urticaria
 - 4. Grade 2 or greater autoimmune reaction
 - 5. Grade 3 injection site reactions
 - 6. Grade 3 anaphylaxis
 - 7. Grade 2 pneumonitis
 - 8. ≥ Grade 3 hematologic toxicities lasting more than 48 hours, including neutropenia, thrombocytopenia and hemorrhage
 - 9. ≥ Grade 3 non-hematologic toxicities
 - 10. Grade 3 neurological symptoms
 - 11. Fever > 41°C, uncontrolled for over 4 hours in the absence of a medical cause
 - 12. Grade 3 diarrhea, Grade 3 skin toxicity, or Grade 3 liver function test increase
 - 13. Evaluation of liver toxicity as defined by Hy's Law:
 - The drug causes hepatocellular injury, generally shown by a higher incidence of 3-fold or greater elevations above the ULN of ALT or AST
 - Total Bilirubin>2xULN, without initial findings of cholestasis (elevated serum alkaline phosphatase)

Efficacy Study Design and Endpoints

The primary clinical endpoint is objective response. A secondary, translational endpoint is increase in the CD8 TIL infiltration in tumor and/or IP washes (pre-treatment vs post-treatment),

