* π is the RLT rate. The minimum acceptable upper bound of a treatment-related RLT is 30%. PP(π > 30%) is the posterior probability that the RLT rate exceeds this 30% upper bound. This posterior probability of an RLT is calculated from the prior distribution, the number of subjects treated and the observed number of treatment-related RLTs.

Using these assumptions, the trial will be suspended if:

4 subjects experience treatment related RLT among the first 6 subjects enrolled or,

5 subjects experience treatment related RLT among the first 9 subjects enrolled or,

6 subjects experience treatment related RLT among the first 12 enrolled etc.

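### The toxicity suspension rule counts every treated patient, including those whose DLT observation is still open, and the 3-week DLT observation is shorter than DLT criterion (b) needs

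*Combined protocol and SAP*

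**What the plan says.** **Suspension rule (Section 8.1, continuous monitoring).** The condition reads "If the posterior probability is .80 or greater that 30% or more of treated subjects experience a treatment related RLT as defined above"; the study is then suspended pending committee review. The prior is Beta(1.2, 2.8). The sentence introducing Table 8 is "The table below describes the number of RLTs per number of treated patients that would trigger suspension", and the table's footnote says that the posterior uses the prior, "the number of subjects treated and the observed number of treatment-related RLTs". The trigger list below the table changes the term: "4 subjects experience treatment related RLT among the first 6 subjects enrolled or", then 5 among the first 9 and 6 among the first 12.

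**DLT definition (Sections 5.2.2 and 8.1).** Most criteria are toxicities arising in cycle 1. Criterion (b) is different: "Any AE leading to a dose delay of greater than 14 days in initiation of cycle 2 will be considered a DLT". Cycles last 21 days (Section 5.2.1).

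**Early stagger (Section 7.1).** The "second patient should not be able to begin treatment until 3 weeks after the first patient has begun the treatment, i.e. completed cycle 1"; the third patient waits for the second in the same way. Section 7.1 adds that "patients should be observed for 3 weeks for DLTs".

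No section defines a DLT-evaluable patient, requires a completed window before a patient enters the denominator, or limits the number of pending patients after the third. RLT is not defined apart from DLT. The rule's reference to a definition above can only mean the DLT list, so I treat the two as the same.

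**The concern.** A posterior built from events and patients treated is sound only if each non-event has been observed as a non-event. Under continuous monitoring, some patients will usually be part-way through observation when an event is reported. If they are in the denominator, each lowers the posterior although nothing has yet been learned about her. The error always runs towards continuing. The practical case is not a suspension being revoked. It is a decisive event reported after further patients have been dosed, so that the trigger does not fire when it should.

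The second issue is one of dates. A patient whose cycle 2 is on hold at 3 weeks has finished the stated DLT observation, yet criterion (b) can still be met.

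**Working it through.** **Inputs.** Prior Beta(1.2, 2.8), cut-off .80, limit 30% and the Table 8 boundaries (Section 8.1); 21-day cycles (Section 5.2.1); up to 45 patients (Section 2.1); enrolment 2018-2019 (Section 1.0), taken as 24 months.

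**1. Reproducing Table 8.** For r events in n patients, PP = P(Beta(1.2 + r, 2.8 + n - r) > .30). Every boundary is the smallest r with PP of at least .80. Thirteen of the 14 printed posteriors match to three decimals. The exception is 4/6, which computes to .922 against the printed .903; the boundary is unaffected.

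**2. Adding pending patients.** Hold r fixed and add k patients who are treated but not yet observed: PP = P(Beta(1.2 + r, 2.8 + n + k - r) > .30).

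Triggers only just met under the .80 rule:
- 3/5 = .843 (suspend); 3/6 = .773 (continue)
- 4/8 = .824; 4/9 = .762
- 5/11 = .812; 5/12 = .757

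Published rows:

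| Row (r/n) | k = 0 | k = 1 | k = 2 | k = 3 |
|---|---|---|---|---|
| 4/6 | .922 | .878 | .824 | .762 |
| 5/9 | .904 | .861 | .812 | .757 |
| 6/12 | .890 | .850 | .804 | .754 |
| 7/15 | .880 | .842 | .799 | .753 |
| 8/17 | .903 | .872 | .836 | .796 |
| 9/20 | .896 | .866 | .832 | .795 |
| 10/23 | .891 | .862 | .829 | .794 |
| 11/26 | .886 | .858 | .827 | .793 |
| 12/29 | .883 | .856 | .826 | .794 |
| 13/32 | .880 | .854 | .825 | .794 |
| 14/35 | .877 | .853 | .825 | .795 |
| 15/38 | .876 | .852 | .825 | .797 |
| 16/41 | .874 | .851 | .825 | .798 |
| 17/44 | .873 | .850 | .826 | .799 |

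One pending patient reverses 0 of 14 rows, two reverse 1 (7/15 to 7/17), and three reverse all 14. For the last row this is arithmetic only, since 44 + 3 exceeds the cap of 45.

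**3. The two readings on the same data.** Suppose that four of the first six patients have an RLT, and the fourth is reported after patients 7 to 9 have been dosed. Read as a fixed cohort, 4 of the first 6 suspends. Read as a running count, 4/9 = .762 does not.

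**4. How many are pending (assumed accrual).** The rate is 45/(24 x 30.4) = .0617 patients per day. If every cycle 2 starts on time, .0617 x 21 = 1.3 patients are pending on average. If 10% wait until day 36, .0617 x (.9 x 21 + .1 x 36) = 1.4; if 30% do, .0617 x (.7 x 21 + .3 x 36) = 1.6.

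**5. Effect on the chance of suspension (simulation, 4,000 trials per setting).** Assumptions: random accrual; the first three starts at least 21 days apart; 30% of DLTs arise through criterion (b) at day 36, the rest evenly over days 1 to 21; Table 8 boundaries, with sample sizes between rows using the next row's count. The Monte Carlo standard error of each probability is at most the square root of .25/4,000 = .008.

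| True rate | Accrual | Running *treated* count | Complete follow-up | Loss (points) |
|---|---|---|---|---|
| 30% | 24 months | .263 | .312 | 4.9 |
| 40% | 24 months | .745 | .776 | 3.1 |
| 50% | 24 months | .967 | .973 | 0.6 |
| 30% | 12 months | .241 | .318 | 7.7 |
| 40% | 12 months | .691 | .754 | 6.3 |
| 50% | 12 months | .967 | .977 | 1.0 |

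At 24 months, the running count treats on average 38.3, 25.7 and 15.7 patients at true rates of 30%, 40% and 50%, against 36.8, 24.0 and 14.5 under the fixed-cohort reading: between one and two more.

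**6. Dates.** With cycle 1 starting on day 1, cycle 2 is due on day 22. A 14-day delay ends on day 22 + 14 = 36, so criterion (b) is met only once day 36 has passed. Section 7.1 stops at 3 weeks, about two weeks short. The 3-day scheduling window in Section 5.2.1 shifts this by up to 3 days.

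**The case against.** The best defence is the trigger list. If the first 6, 9 and 12 patients are fixed cohorts, later patients cannot undo a met boundary, and a late event only delays suspension. That reading is available and, if adopted, removes the dilution by later patients. But the introductory sentence and the table footnote describe a running count of treated patients. Even the fixed reading does not say whether the last patient in a cohort must have been observed.

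The published rows also have some slack: a single pending patient reverses none of them. That stands, although the text rule applies the .80 cut-off continuously, not only at the tabulated sample sizes. It is also fair that most serious toxicities are already cycle-1 DLTs, so criterion (b) may add few events, and that Sections 8.1 and 5.7 allow suspension or termination on other safety grounds. Neither point repairs the denominator, because patients still in cycle 1 dilute it too.

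Four stronger inferences should be resisted.
- *Suspension is missed mainly when toxicity is high.* The simulated loss is largest near the 30% limit and one point or less at 50%.
- *One pending patient routinely disables the rule.* This happens only where the trigger is just met, and on no published row.
- *Every patient stays pending for 36 days.* That would give .0617 x 36 = 2.2 pending on average, but a patient who starts cycle 2 on time is resolved at about day 22.
- *Patients never dosed are counted.* The rule, the table title and the footnote all say treated; *enrolled* appears only in the trigger list and is better read as inconsistent wording.

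**Conclusion.** The concern holds in limited form and should be fixed. The rule does not require completed DLT observation, and its two wordings can give opposite decisions on the same data. Under the running reading, one pending patient can mask a just-met trigger, and three reverse every published row (13 of 14 being reachable with 45 patients). The expected effect is modest: about 3 to 5 points of suspension probability at true rates of 30-40% under 24-month accrual, about 6 to 8 points if accrual took 12 months, and one point or less at 50%, always towards continuing. These sizes rest on the assumed accrual and on a 30% share of criterion (b) events, neither of which the documents give. The posterior calculations rest only on the SAP's own prior and cut-off.

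The conflict between the 3-week observation and criterion (b) needs no assumption beyond the stated cycle length.

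**What to change.** In Section 8.1, define the denominator as patients who have had a DLT/RLT or whose DLT status is final, meaning that cycle 2 has started or the criterion (b) limit has passed. Use that one term in the rule, Table 8, its footnote and the trigger list, in place of *treated* and *enrolled*. State that RLT means DLT, if that is intended.

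Separately, the sponsor must reconcile the 3-week observation and stagger in Section 7.1 with criterion (b) in Sections 5.2.2 and 8.1. How to do so is a clinical decision for the sponsor.

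The denominator change is one of wording, with no extra patients or procedures; the Table 8 boundaries need not change. Its cost is a slightly higher chance of suspension, including when the true rate is exactly 30% (.263 to .312 in the 24-month simulation, under complete follow-up). A suspension leads to committee review, not automatic closure.
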